Title: Digital Escape Room Game for Hypovolemic Shock Management: A Mixed-Methods Study in Nursing Education

NCT number: NCT07204899

Date of the document (reviewed by a human subjects protection review board): 6.05.2025

Study Protocol:

Methods

Study design

This study employed an explanatory sequential mixed-methods design. A randomized controlled trial design was used in the quantitative phase. The experimental group participated in an online escape room intervention, while the control group received traditional lecture-based instruction. Quantitative data were collected to evaluate the effect of the intervention on students' knowledge level and satisfaction.

Following the quantitative phase, a purposive sample of students from the experimental group was invited to participate in focus group interviews. The qualitative phase was conducted to explore students' perceptions and experiences in greater depth, providing contextual insights into the mechanisms underlying the quantitative results. Integrating the two phases allowed for a more comprehensive understanding of the educational impact of the online escape room intervention, combining measurable outcomes with rich narrative accounts.

Setting and participants

The study was conducted between June and July 2025 with third-year nursing students enrolled at a foundation university in Ankara, Türkiye. Students were invited to participate through an in-class announcement, and the inclusion criterion was being a third-year nursing student who provided informed consent.

Power analysis was performed using G*Power 3.1 (F tests, repeated measures ANOVA—between-group effect). Based on two groups and three measurement points, a

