repeated measures correlation of 0.50, an effect size of $f=0.35$, a two-way $\alpha=0.05$, and a power of $1-\beta=0.80$, the required total sample size was calculated as $N=46$ (23 participants in each group). Considering possible attrition, a total sample size of 30 participants was planned for each group. Accordingly, 58 volunteer students were recruited for the quantitative phase and randomly assigned to either the intervention or control groups. For the qualitative phase, 12 students were purposively selected from among those who had participated in the quantitative phase. In addition, nurse educators with at least five years of experience in teaching and mentoring students were included as participants. Data collection for the qualitative phase was carried out through focus group interviews and continued until no new themes emerged, indicating thematic saturation.

Randomisation and Blinding

Eligible participants were randomly assigned to either the experimental group, which received the digital escape room game intervention, or the control group, which received traditional classroom-based education, in a 1:1 allocation ratio. Randomisation was performed using an online random sequence generator (Research Randomizer, <https://www.randomizer.org/>) by an independent statistician who was not involved in participant recruitment, intervention delivery, or outcome assessment.

Given the nature of the interventions, blinding of participants and facilitators was not feasible. However, to minimise performance and detection bias, outcome assessors and data analysts remained blinded to group allocation throughout the study. All data were coded anonymously, and statistical analyses were conducted using coded identifiers (Group A/Group B) until the final interpretation phase.

Pre-application of the study

A preliminary application was undertaken to assess the clarity, feasibility, and functionality of both the data collection instruments and the digital escape room game. This

stage was conducted with 10 fourth-year nursing students enrolled in the 2024–2025 academic year. Participants were asked to complete the data collection forms, engage with the escape room game, and provide structured feedback regarding the comprehensibility of the forms, the usability of the game design, and the alignment of tasks with the intended learning outcomes.

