of the discussions. The interview form consisted of four open-ended questions addressing participants' expectations prior to the game and whether these were fulfilled, the emotions they experienced during the activity, the game's contribution to their learning (e.g., knowledge, practical skills, decision-making), and their opinions on the broader use of digital escape room games in nursing education. The discussions explored not only students' experiences and perceptions of the usefulness of the HYPSEM game, but also their suggestions for areas of improvement. Each focus group included three to five participants and lasted between 45 and 80 minutes. All sessions were audio-recorded and subsequently transcribed verbatim.

Statistical Analysis Plan (SAP):

Quantitative data analyses were conducted using IBM SPSS Statistics version 25. Descriptive statistics (mean, standard deviation, minimum, and maximum) were calculated for all study variables. The internal consistency of the GAMEX scale and its subdimensions was assessed using Cronbach's α coefficients.

To evaluate baseline equivalence between groups, independent samples t -tests were performed. The effectiveness of the intervention over time was examined using a repeated-measures analysis of variance (ANOVA) with one within-subjects factor (time: pre-test, post-test 1, post-test 2) and one between-subjects factor (group: GAMEX vs. control). Mauchly's test of sphericity was applied to verify the assumption of sphericity, and where violations occurred, the Greenhouse-Geisser correction was used. Effect sizes for ANOVA results were reported as partial η^2 .

In addition, Bonferroni-adjusted pairwise comparisons were conducted to explore differences across the three time points within each group. Independent samples t -tests were also carried out at each measurement point to assess between-group differences. For these comparisons, Cohen's d values were calculated to estimate the magnitude of differences (0.2 = small, 0.5 = medium, 0.8 = large). Statistical significance was set at $p < .05$ for all analyses.

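### The post-test group differences and Cohen's d come from t-tests that leave out the pretest; ANCOVA on the pretest would estimate them more precisely unless the pretest-posttest correlation is low.

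*Combined protocol and SAP*

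**What the plan says.** The SAP gives the main analysis of effectiveness to a group-by-time model: "The effectiveness of the intervention over time was examined using a repeated-measures analysis of variance (ANOVA) with one within-subjects factor". The pretest is one of its three time levels, and its results are summarised by partial eta-squared. Two sets of follow-up comparisons are planned. The first is within group: "Bonferroni-adjusted pairwise comparisons were conducted to explore differences across the three time points within each group". The second is between groups: "Independent samples t -tests were also carried out at each measurement point to assess between-group differences". For this second set, Cohen's d "values were calculated to estimate the magnitude of differences". On the threshold the SAP says: "Statistical significance was set at $p < .05$ for all analyses".

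No model in the document uses the pretest as a covariate, and no confidence intervals are mentioned.

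The section on the implementation phase places the pretest before the lecture and the lecture before allocation, so a pre-allocation score exists for every student. It adds that allocation made the groups' mean pretest knowledge similar. The section on randomisation describes only an online sequence generator run by an independent statistician and does not mention pretest scores.

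**The concern.** The t-tests and their d values are the only planned between-group estimates at a given post-test. They are therefore what a reader will use to judge how large the effect is and whether it lasts a month. They leave out a score that was measured before allocation and probably predicts the outcome. With 55 students, precision is scarce.

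The repeated-measures ANOVA does not fill the gap. It uses the pretest, but it tests the pattern over time and yields no adjusted difference at either post-test.

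The wording on comparable pretest means adds a second reason. If pretest scores really constrained the allocation, a t-test that ignores them uses a standard error that is too large.

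**Working it through.** **Inputs from the documents.** 27 intervention and 28 control students (implementation phase). Two groups, three measurements, correlation 0.50, f = 0.35, alpha 0.05, power 0.80, required N = 46 (setting and participants).

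**Assumptions.** Normal scores, equal SDs, and the same correlation rho between any two tests. The 0.50 is a planning value, so rho is varied from 0.1 to 0.7. Differences are in units of the post-test SD.

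**1. The plan's own figure.** The stated test is "F tests, repeated measures ANOVA—between-group effect". Its noncentrality is lambda = f² × N × m / (1 + (m − 1) × rho), with m = 3.
- N = 46: 0.1225 × 46 × 3 / 2 = 8.45, power 0.811.
- N = 44: 0.1225 × 44 × 3 / 2 = 8.09, power 0.793.

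So N = 46 reproduces. It follows that f refers to the group difference averaged over three time points: 2 × 0.35 = 0.70 SD on average. If the pretest difference is zero and the effect is equal at both post-tests, that is 0.70 × 3 / 2 = 1.05 SD at each.

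**2. Interval width at one post-test.**
- t-test: SE = √(1/27 + 1/28) = 0.2697; half-width = 2.006 × 0.2697 = 0.541 (53 df).
- ANCOVA: SE = 0.2697 × √((1 − rho²)(1 + 1/51)), where 1/51 = 1/(55 − 4) allows for chance pretest imbalance. At rho 0.50 this is 0.2697 × √(0.75 × 1.0196) = 0.2359; half-width = 2.007 × 0.2359 = 0.473 (52 df).
- Equivalent t-test sample: 55 / ((1 − rho²)(1 + 1/51)).

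| rho | ANCOVA half-width | Ratio to t-test | Equivalent t-test N |
|---|---|---|---|
| 0.1 | 0.544 | 1.005 | 54 |
| 0.14 | 0.541 | 1.000 | 55 |
| 0.2 | 0.535 | 0.990 | 56 |
| 0.3 | 0.521 | 0.964 | 59 |
| 0.5 | 0.473 | 0.875 | 72 |
| 0.7 | 0.390 | 0.721 | 106 |

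These are expected widths. In simulation the ANCOVA interval was the narrower one in about 99% of trials at rho 0.5, 79% at 0.3, 55% at 0.2 and 30% at 0.1. At rho 0.2 to 0.7 coverage was about 95% for both methods.

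**3. Whether the ANOVA already supplies the gain.** The group-by-time contrast works on change scores, whose variance is 2(1 − rho) = 1.00 times the post-test variance at rho 0.50, against 1 − rho² = 0.75 for ANCOVA. The group main effect averages in the pretest, where no treatment difference is expected. So it does not.

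**4. Power at one post-test (two-sided 0.05, rho 0.50).**
- 1.05 SD: t-test 0.97, ANCOVA 0.99.
- 0.70 SD (assumed): t-test 0.72, ANCOVA 0.83 (0.75 at rho 0.3, 0.94 at rho 0.7).

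**5. If allocation was constrained on the pretest.** No limit is stated, so the absolute pretest difference was capped at 0.1, 0.25 or 0.5 SD. At rho 0.50 with no true effect, a single t-test rejects about 2.5%, 3.1% and 4.2% of the time. ANCOVA stays close to 5%.

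**6. Two post-tests.** With no true effect, at rho 0.50, the chance of at least one false positive is about 9% if the two t-tests stand alone, and 1.6% if they are read only after a significant interaction. Two ANCOVAs with Holm give about 5%. Holm costs power when only one post-test has an effect. For 0.70 SD at one post-test, ANCOVA with Holm has power 0.74 to 0.75 at rho 0.5 (simulation runs differ slightly), 0.65 at 0.3 and 0.63 at 0.2, against 0.72 for the planned t-test.

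**The case against.** The best defence is that nothing here is an error. The SAP assigns effectiveness to the ANOVA, which does include the pretest; the t-tests are follow-up, and an unadjusted d sits naturally beside the small, medium and large benchmarks that the SAP lists. The gain also rests on an unknown correlation. The form is a 20-item true-false test with expert content review but no reported reliability, a lecture separates pretest from post-test, and the second post-test is a month later. These points stand, and they limit the concern to precision.

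Four stronger readings are tempting, and the documents do not support them.
- **The t-tests are biased or invalid.** Under simple randomisation they are neither. Under constrained allocation they are conservative.
- **The SAP ignores the pretest.** It uses it as a time level and in the baseline comparison. The gap is confined to the post-test differences and d.
- **ANCOVA always gives a narrower interval.** It does so on average only above a correlation of about 0.14, and at 0.2 the gain is about 1%.
- **The error rate is about 9% and Holm is required.** That figure applies only if the t-tests stand alone. The SAP does not say whether they depend on the ANOVA.

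The constrained-allocation results also depend on assumed limits. The wording about comparable means may simply describe how the groups turned out.

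**Conclusion.** The concern holds as an avoidable loss of precision in the estimates that will carry the size and durability of the effect. At the plan's correlation of 0.50, the expected 95% CI half-width at each post-test is 0.54 SD as planned and 0.47 SD with the pretest as covariate, which is what about 72 students would give in a t-test instead of 55. The gain grows to 0.39 SD at a correlation of 0.7, shrinks to almost nothing at 0.2, and turns into a loss of about 0.5% at 0.1.

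A reader might infer that the trial is underpowered for its post-test comparisons. At the effect the plan itself implies, 1.05 SD, it is not: power is already 0.97. The rise from 0.72 to 0.83 applies to an assumed 0.70 SD per post-test.

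The change is worth making because it costs almost nothing and because ANCOVA keeps close to its nominal level under either account of allocation that was examined. That check used normal scores and a symmetric cap on the pretest difference, so other allocation procedures remain untested.

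**What to change.** Replace the two post-test t-tests with ANCOVA of post-test score on group with pretest as covariate, or with one mixed model over both post-tests with the pretest as covariate. Report adjusted differences with 95% CIs. For d, divide the adjusted difference by the pooled post-test SD; dividing by the ANCOVA residual SD would enlarge d by 1/√0.75 = 1.155, about 15%, at a correlation of 0.50. Keep the group-by-time ANOVA. State the observed pretest-posttest correlations, and say whether pretest scores were used in allocation, since the sections on randomisation and implementation describe it differently.

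The SAP is written in the past tense. If results have been seen, label the adjusted analysis as added and report it beside the planned t-tests.

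The cost is one degree of freedom and a negligible loss if the correlation is very low. No new data are needed.

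Separately, the authors should say whether the post-test comparisons depend on the ANOVA result. Holm across the two is optional: it brings the false-positive chance to about 5%, but at low correlations it can take power below that of the planned t-test when only one post-test has an effect.

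### No deciding between-group comparison is named and none is adjusted, so the chance of a false efficacy finding is about 9% to 14% under simple randomisation, not 5%

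*Combined protocol and SAP*

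**What the plan says.** Under Statistical Analysis Plan (SAP), the effect of the intervention over time is examined by a repeated-measures ANOVA with three time points and two groups. This model yields two terms that bear on the intervention: group, and group by time. Neither is named as decisive.

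The same section then lists two further sets of tests on the knowledge score:

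- within groups: "Bonferroni-adjusted pairwise comparisons were conducted to explore differences across the three time points within each group";
- between groups: independent t-tests that "were also carried out at each measurement point to assess between-group differences", each with its own Cohen's d.

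The threshold is common to everything: "Statistical significance was set at $p < .05$ for all analyses". No primary outcome, test or time point is named, and the t-tests are not made conditional on a significant ANOVA result.

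The power analysis, under Setting and participants, is for the ANOVA between-group effect, with f = 0.35, a "repeated measures correlation of 0.50", alpha 0.05 and power 0.80, giving N = 46. Under Implementation phase of the study, both arms receive the two-hour lecture, both complete the same knowledge form at pretest and at two post-tests, and the group sizes are 28 (control) and 27 (intervention).

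**The concern.** The question is whether the game adds knowledge beyond the lecture. Only comparisons between arms answer it. A rise within one arm mixes the lecture, repetition of the same 20 items and, in one arm, the game. The one multiplicity correction in the plan therefore protects comparisons that do not isolate the game's effect, and the comparisons that do have no protection.

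As written, a significant result at the immediate post-test, at the one-month post-test, in the group term or in the interaction could each be reported as effectiveness at p < .05. Significance within one arm but not in the other could also be misread as an effect of the game.

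**Working it through.** **Inputs.** From Setting and participants: alpha 0.05, f = 0.35, correlation rho = 0.50, three time points, N = 46. From Implementation phase of the study: n = 27 and 28. From the SAP: p < .05 throughout. Assumptions: normal scores and equal correlation between time points.

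**1. The plan's own figure.** For the between-group effect, lambda = N f² m / [1 + (m − 1) rho], with 1 and N − 2 degrees of freedom.

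- N = 44: lambda = 44 × 0.1225 × 3 / 2 = 8.09; power 0.793.
- N = 46: lambda = 46 × 0.1225 × 3 / 2 = 8.45; power 0.811.

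The smallest even N with power of at least 0.80 is 46, as stated. The calculation is for one test at 0.05.

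**2. Which tests count.** GAMEX was given only to the intervention arm, so it adds no between-group test. The pretest t-test precedes the game and cannot support an efficacy claim, so it is left out. Four tests remain: two post-test t-tests and two ANOVA terms.

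**3. Bound for two tests.** If independent, 1 − 0.95² = 9.75%. Correlation between the post-tests lowers this somewhat.

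**4. Simulation, simple randomisation.** 200,000 trials per setting with no true effect, n = 27 and 28, each test at 0.05. Chance of at least one p < .05:

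| Tests counted | rho = 0.5 |
|---|---|
| One pre-named test | 4.9% |
| Two post-test t-tests | 9.0% |
| ANOVA group or interaction | 9.6% |
| Two post-tests plus interaction | 12.3% |
| Two post-tests plus both ANOVA terms | 13.6% |

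Over rho from 0 to 0.9, the two post-tests run from 9.8% down to 7.2%, and the four tests from 14.6% down to 11.8%.

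**5. If allocation was matched on pretest.** When pretest means are balanced by design, the post-test mean difference has about (1 − rho²) of the variance that the unadjusted t-test assumes. At rho = 0.5 that is 0.75, so each test's real size is about 2Φ(−1.96/√0.75) = 2Φ(−2.26) = 2.4%. Simulated with matched pairs, the two post-tests together give about 5%, and about 6% to 7% with the ANOVA terms added. At rho = 0.3 the figures are about 8% and 8.5%; at rho = 0.7, about 2% and between 4% and 5%. Conservative single tests are masking the multiplicity. Two pretest-adjusted (ANCOVA) post-tests at 0.05 give 9% to 10% with or without matching.

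**6. After correction.** Under the global null, Holm errs only if the first step, at 0.025, is passed. At rho = 0.5 the chance is 4.6% with two t-tests and 4.8% with two ANCOVA tests.

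**The case against.** **An implied main analysis exists.** The SAP links effectiveness to the ANOVA, introduces the t-tests as additions, and the trial is sized on the ANOVA between-group effect. This stands in part: a reader might infer that the plan puts all tests on one footing, and that goes too far. But the SAP does not carry the powered effect forward as the deciding one, and the two ANOVA terms alone give 9.6%. Had the post-tests been read only after a significant interaction, the joint rate under the global null would be 1.6%; no such gate is stated.

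**Allocation may have been balanced on pretest.** Implementation phase of the study says that assignment secured comparable pretest means. On that reading the unadjusted set is close to nominal at rho = 0.5. This stands as a condition on the size. Randomisation and Blinding describes only an online sequence generator, so matching cannot be assumed, and the near-nominal rate disappears once the analysis is adjusted for pretest.

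**The upper figure could be put higher.** Counting all three t-tests with both ANOVA terms gives 15.6%, and a reader might quote an error of 16%. The extra test is the pretest comparison, which no one could claim as an effect of the game. The documents support about 14% as the upper figure at rho = 0.5.

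**Conclusion.** The point holds. The plan has an implied main analysis but does not name its deciding term, and it adds between-group tests that are neither gated nor adjusted. At the plan's own correlation of 0.50, with 27 and 28 students and simple randomisation, the chance of at least one false efficacy finding is about 9% (two post-tests) to 14% (with both ANOVA terms). If allocation was truly matched on pretest, the unadjusted set gives about 5% to 7% at that correlation. The documents do not settle which applied.

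Pretest adjustment alone would not remove the problem. It would also be wrong to infer that naming a primary comparison now restores 5%: the text is in the past tense, gives final group sizes and dates data collection to June and July 2025, so such a choice might follow sight of the results. The trial is not invalidated; its effectiveness claim lacks the error rate that its threshold implies.

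**What to change.** Apply Holm across the two post-test between-group comparisons, preferably each adjusted for pretest. Treat the ANOVA group and interaction terms as supportive. Drop the pretest t-test from the inferential set, and label the within-group pairwise tests descriptive.

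If the data have already been analysed, report all between-group tests, give Holm-adjusted p-values and state that no primary comparison was pre-specified, rather than naming one afterwards. Also state how comparable pretest means were obtained, since the size of the problem depends on it.

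Cost: a short change to the SAP and some power. The planned f = 0.35 corresponds to d = 2 × 0.35 = 0.7 for two groups. At d = 0.7 and rho = 0.5, ANCOVA power for one post-test falls from about 83% at 0.05 to about 75% at Holm's first step of 0.025. That is a floor, because the second comparison is tested at 0.05 once the first succeeds; with d = 0.7 at both post-tests, the chance of detecting at least one is about 90%. Even the floor exceeds the 72% of the planned unadjusted t-test at 0.05. This is a cheap improvement.
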